COVER PAGE

Study Title: Prospective RCT Of Water Exchange (WE) vs. WE Plus Cap-Assisted Colonoscopy

Unique Protocol ID: GAST-015-16S

ClinicalTrials.gov ID: NCT03160859

Document Dates: Protocol & Statistic Analysis (as approved): 8/14/2017

Record Verification: October 2023

Overall Status: Completed

Study Start: June 8, 2018 [Actual]

Primary Completion: October 28, 2022 [Actual]

Study Completion: October 28, 2022 [Actual]

Sponsor: VA Office of Research and Development

Responsible Party: Sponsor

Collaborators: (1) VA Northern California Health Care System; (2) VA Palo Alto Health Care System

Abbreviated Protocol - Submitted To DMC

TITLE: PROSPECTIVE RCT OF WATER EXCHANGE (WE) VS. WE PLUS CAP-ASSISTED COLONOSCOPY

PI: [name]

PROTOCOL

I. Introduction

The purpose of this study is to compare two different, but normally, used methods of colonoscopy in patients examined by the water exchange (WE) method alone versus water exchange plus a transparent cap. This study involves the use of an FDA approved, commercially available and clinically used, transparent cap that will be fitted onto the end of the colonoscope at the tip. The aim of this study is to determine which method (with or without cap) is more effective in diminishing pain during the insertion of the colonoscope.

This will be a multi-VA site, unblinded investigators, prospective random control trial (RCT). Randomization (WE, WE + regular transparent cap) will be based on computer generated random numbers placed inside opaque sealed envelopes. The envelope (in pre-arranged order) will be opened to reveal the code when the colonoscopist is ready to insert the endoscope to begin the examination.

There are two arms or groups to this study: WE (water exchange) control group and WECAC (water exchange plus transparent cap placed at tip of the colonoscope) group which will use water plus a cap instead of air.

- Control Method (WE): This group will have the air in the colon removed and replaced with water to guide the insertion of the colonoscope.
- Study Method (WECAP): This group will use water instead of air plus the transparent cap fitted onto the end of the colonoscope.

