The goals are to determine if WECAC significantly reduces real-time maximum insertion pain (RTMIP) in both genders, to identify baseline patient-and procedure characteristics that predict low RTMIP, and to assess impact of WECAC on secondary outcomes. An additional goal is to develop pilot data to assess the hypothesis that WECAC, by increasing proximal colon ADR, can reduce the occurrence of post colonoscopy colon cancer (interval cancer) particularly in the proximal colon. This long term objective in the unsedated Veterans will be facilitated by identifying the least painful insertion method.

Patients who are willing to participate will sign an informed consent before starting the colonoscopy procedure. Separate parallel randomization will be set up at each site, stratified by investigator and type of colonoscopy (screening or surveillance). All subjects will have been scheduled for unsedated colonoscopy as a result of lack of escort or personal preference.

This multi-site study is designed to enroll 256 participants in total. Up to 150 patients are anticipated to enroll from the VA Greater Los Angeles Healthcare System. The performance

Version: 8/2016 1

site at the WLAVA will be in building 500, 5 East Clinical Procedure Center. The other study sites include: Sacramento VAMC and Palo Alto/Livermore VAMC.

This study is expected to take up to 5 years to complete. The expected duration of the patient's participation in this study is 1 hour for the colonoscopy procedure.

II. Screening Procedure

Patients will have already been scheduled for the colonoscopy procedure as part of their standard care. The patient will have received instructions for the standard preparation of the unsedated colonoscopy along with a flyer identifying and explaining the research study. The flyer will instruct the patient to call either the PI or the Study Coordinator for more information on the study if he/she is interested in participating.

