
(b) Hypotheses

Primary Hypothesis: Real-time maximum insertion pain (RTMIP) is significantly lower in both male and female Veterans examined by WECAC compared with WE.

Secondary Hypotheses: WECAC will show a significantly higher proportion with no pain, shorter insertion time and higher proximal colon ADR than WE alone in both male and female Veterans.

Exploratory hypotheses: Co-variables affect Veterans' report of RTMIP.

(c) Specific Objectives

a. To determine if WECAC significantly reduces RTMIP in both genders, to identify baseline patientand procedure characteristics that predict low RTMIP, and to assess impact on secondary outcomes. b. If WECAC increases *proximal colon* ADR, we will prepare for a multi-site VA cooperative study. The goal is to assess the hypothesis that WECAC, by increasing *proximal colon ADR*, can reduce the occurrence of post colonoscopy colon cancer (interval cancer) particularly *in the proximal colon*. This long term objective in the unsedated Veterans will be facilitated by identifying the least painful insertion method.

(2) Background and Significance (a) Background

Colonoscopy with air began without sedation. Insertion pain limited success in ~20% (13,23,24). Widespread use of sedation followed (13,23,24). In for-profit settings, anesthesiologist administered propofol is a major revenue stream; but has attracted criticisms (28). The VA focus on patient-centered care, teaching, efficacy, efficiency, and research data to support the mission, underpin efforts to discover technique(s) to attenuate RTMIP in unsedated Veterans. High quality (29) [higher proportion completing colonoscopy with no pain, shorter insertion time, proximal colon ADR] further strengthens appeal.

Factors linked to increased pain in unsedated cases reviewed by the PI (30) include: female, low body mass index (BMI) (≤25), female with low BMI, younger age (≤40 or ≤20 years), older age (>80 years), anxiety and anticipating discomfort; history of abdominal surgery, diverticulosis, diverticulitis, incomplete colonoscopy, and irritable bowel; difficult anatomy, inflammatory bowel symptoms, technically difficult insertion, lower gastrointestinal bleeding, obstructing malignancy, and following gastroscopy.

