Exclusion criteria. Decline to be randomized, unable to give consent or respond to questionnaires, history of colon surgery, active inflammatory bowel disease, lower gastrointestinal bleeding (except for occult blood or FIT positive in the context of colon cancer screening), therapeutic colonoscopy (e.g., hemostasis, removal of large polyp), proctosigmoidoscopy, bidirectional endoscopy, inadequate consumption of bowel preparation, known history of severe diverticulosis or diverticulitis, history of abdominal surgery previously requiring sedation for colonoscopy, current narcotic/anxiolytic medication use, prior unsuccessful experience with unsedated colonoscopy, emergent colonoscopy, evidence of colonic obstruction based on pre-colonoscopy clinical evaluation, current participation in other studies, medical condition that could increase the risk associated with colonoscopy (e.g., active cardiac or pulmonary disease or other serious disease), medical condition that would preclude a benefit from colonoscopic screening (e.g., cancer or any terminal illness), prosthetic heart valve, anticoagulant therapy, nonmedical problems (e.g., psychiatric disorders, excessive use of alcohol), need for special precautions in performing colonoscopy (e.g. antibiotic prophylaxis), and request of on demand sedation.

Primary outcome measure (for male and female subjects).

	_
Real time maximum insertion	_
pain (RTMIP) (unblinded) score	
(validation by correlation with	
recalled pain described below)	

Pain during insertion reported to the unblinded assisting nurse, visual analogue scale, VAS: 0=none, 10=most severe. The highest pain score will be tabulated for analysis. Timing of data collection will be at the discretion of the nurse to minimize bias by colonoscopist behavior.

Secondary outcome measures (for male and female subjects).

Proportion with no insertion pain Proportion report no pain during insertion of the colonoscope. Quality marker.

Insertion time	Time to cecum (clock display on monitor). Faster insertion is a quality marker
Proximal colon ADR	ADR from cecum to splenic flexure. Measure of high quality colonoscopy

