Updated male Veteran sample size. Pilot data in scheduled unsedated male Veterans were updated. The real time maximum insertion pain (RTMIP) [mean (SD)] was 2.7 (2.2) with WE (n=87) and 1.5 (2.1) with WECAC (n=38). The reduction (44%) 2.7-1.5=1.2 is 1.2/2.2=0.55 standard deviation (SD) units. The sample size/group needed to detect a difference at a level of significance of 0.0492 (adjusted for Obrien-Fleming interim stopping rules, one interim analysis at 50% completion) with 90% power is 72 or 144 total using a twosided two sample t-test. Assuming 90% of subjects will be evaluable, we plan to recruit 160 male Veterans. Updated pilot data showed the PI performed 30 scheduled unsedated colonoscopies (male) in 1 year when ~2200 colonoscopies were offered at VAGLAHS (1.36%). At participating sites, a total of ~9000 colonoscopies (VAGLAHS 2200, VANCHCS 3300, VAPAHCS 3500) will be performed each year. For purpose of conservative estimation, 1/2 of 1.36% (0.68%) of all colonoscopies will be presumed to be in scheduled unsedated male Veterans when the option is made available up front. In 51 month (4.25 year) enrollment period, a total of 38250 colonoscopies will be performed. 260 (0.68% of 38250) male Veterans will receive scheduled unsedated colonoscopy, making target enrollment of 160 achievable (only 160/260 = 62% enrollment rate needed). In support of this possibility, in two prior RCT in scheduled unsedated male Veterans at VAGLAHS and VANCHCS comparing WE vs. air colonoscopy, high enrollment rates of 97.7% (84/86) and 95.2% (100/105), respectively, were recorded. Sample size of 160 will be sufficient to show significant differences in some of the previously listed secondary outcomes related to quality colonoscopy in

Secondary outcome power estimates based pilot data in WE (n=87) and WECAC (n=38) in male Veterans					
Secondary Outcomes	Pilot (WE vs. WECAC)	Difference (SDU or %)	Sample size per group needed*		
Recalled pain, score (SD)	1.5(2) vs. 0.5(2)	1 (0.5 SDU)	84 (Will be dropped)		
Successful cecal Intubation	98% vs. 100%	2%	(Will be dropped)		
Proportion with no pain	18% vs. 46%	28%	54		
Insertion time, minutes (SD)	15(5) vs. 12( 5)	-3 (0.6 SDU)	58		
Overall ADR - entire colon	36% vs. 50%	14%	258		
Proximal colon ADR	17% vs. 40%	23%	76		
Right colon ADR	20% vs. 40%	20%	106		
Willing to repeat, score (SD)	9.0(2.5) vs. 9.6(0.9)	0.6 (0.4 SDU)	(Will be dropped)		

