ADR, adenoma detection rate; SD, standard deviation; U, units. *90% power, 95% confidence or 5% α error level.					

male Veterans (e.g. proportion with no pain, insertion time, proximal colon ADR). The remaining previously listed secondary outcomes in male Veterans will be dropped (e.g. recalled pain, successful cecal intubation, overall and right colon ADR, willing to repeat).

Updated female Veteran sample size. After receipt of the critique, the PI identified 9 scheduled unsedated female Veterans (5 WE, 4 WECAC). RTMIP were WE, 6.2 (3.5) and WECAC, 3.5 (3.7). The reduction (44%) was 2.7/3.7 or 0.7 SD unit. The female Veterans had significantly higher RTMIP than the male Veterans when examined by WE, but the percent reduction of RTMIP by WECAC was equivalent (44%). The sample size/group needed to detect a difference at a level of significance of 0.0492 (adjusted for Obrien-Fleming interim stopping rules, one interim analysis at 50% completion) with 90% power is 43 or 86 total using a two-sided two sample t-test. Assuming 90% of subjects will be evaluable, we plan to recruit 96 female Veterans. Sample size of 96 will be sufficient to show significance in differences in some of the previously listed secondary outcomes related to quality colonoscopy in female Veterans (e.g. proportion with no pain, insertion time, overall and segmental ADR). The remaining previously listed secondary outcomes in female Veterans will be dropped (e.g. recalled pain, successful cecal intubation, willing to repeat).

Secondary outcome power estimates based pilot data in WE (n=5) and WECAC (n=4) in female Veterans					
Secondary Outcomes	Pilot (WE vs. WECAC)	Difference (SDU or %)	Sample size per group needed*		
Recalled pain, score (SD)	3.1(3) vs. 1.6(3)	1.5 (0.5 SDU)	84 (Will be dropped)		
Successful cecal Intubation	100% vs. 100%	0%	(Will be dropped)		
Proportion with no pain	0% vs. 25%	25%	32		
Insertion time, minutes (SD)	17(4.5) vs. 14(4.5)	-3 (0.7 SDU)	43		
Overall ADR - entire colon	20% vs. 50%	30%	48		
Proximal colon ADR	20% vs. 50%	30%	48		
Right colon ADR	20% vs. 50%	30%	48		
Willing to repeat, score (SD)	9.2(1.1) vs. 9.5(1.0)	0.3 (0.3 SDU)	233 (Will be dropped)		
ADR, adenoma detection rate; SD, standard deviation; U, units. *90% power, 95% confidence or 5% $\alpha$ error level.					

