In both male and female Veterans, record will be kept of all these variables, however, to demonstrate comparability of the study and control groups. When the male and female data are combined, the sample size may reveal differences between WE and WECAC that are worth pursuing, thus providing pilot data for future studies (e.g. overall and segmental adenoma detection rates in scheduled unsedated subjects).

Statistical Analysis. Analysis will be performed based on assigned groups using STATA software (StataCorp 2013. Stata Statistical Software. College Station, TX: StataCorp LP). Descriptive statistics (frequencies, measures of central tendency and dispersion) will be used to evaluate the distribution of each variable. Data as mean (SD) or median (IQR) will be assessed by 2-samples independent samples tests (e.g. Student's t), Fisher exact test; relative risk tests and correlation analysis will be used to evaluate hypotheses. P<0.05 will be considered significant. Statistical assumptions required will be checked and appropriate data transformations or non-parametric test (e.g. Wilcoxon-Mann-Whitney *U test*,) will be used if assumptions are not met. Linear regression will be used to determine significant factor(s) that impact on the primary outcome. The analysis will use intention-to-treat principles, i.e., all randomized patients will be included in the analysis even if their colonoscopies were discontinued early (e.g., pain, poor preparation). The pain score at discontinuation will be used for the analysis for patients with early discontinuation.

Hypotheses Testing. There will be one-interim analysis and a final analysis for this study. The interim analysis will be conducted after 50% of subjects have been evaluated. This interim analysis will be for the primary analysis alone. The significance level for the interim analysis will be 0.0054 based on the standard O'Brien-Flemming rule. The study will be stopped if there is a significant result for the interim analysis. The final analysis will use a 0.0492 level of significance.

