Primary hypothesis. Real-time maximum insertion pain (RTMIP) is significantly lower in the patients examined by the WECAC technique compared with the WE technique. The analysis will compare 2 groups (WECAC vs. WE) with a two sample t-test. If the data show substantial non-normality (as in a prior dataset with WE (5)); we will compare the groups with a Mann-Whitney *U* test; P<0.0492 considered significant. Secondary analysis of the primary outcome will utilize mixed effects regression models to evaluate the effects of potential covariates/confounds described in Tables 9 and 10. First, we will assess the effect of each individual covariate in regression models including the effect for group assignment and gender (stratification factor in the randomization), as well as the covariate by group interaction. Next, we will construct a multiple regression model with the set of covariates found to be significant (either as a main effect or an interaction effect) in an overall regression model along with group assignment.

Dependent Variables	Variable Type	Analysis method
Primary Outcome		
RTMIP (0=none,	Continuous	2 sample Student t test. However, if distribution of the data is skewed as
10=most severe)	Continuous	seen in an earlier study (5), the Mann-Whitney U test will be used.

We have updated the analytic plan to include multi-level random effects (hierarchical model) for study site and provider within site. We will include two levels of random effects in this model: 1. random effects for study site, 2. random effects for provider which will be nested within sites.

Secondary hypotheses. WECAC produces significantly higher quality colonoscopy outcomes. For example, when WE alone and WECAC are compared, the proportion completing colonoscopy with no pain, insertion time, and ADR in the proximal colon will be significantly different. For continuous secondary outcomes (e.g. insertion time), we will use a similar analysis strategy as that used for the primary outcome. For dichotomous secondary outcomes (e.g., no pain, proximal colon ADR) we will use Chi-square tests to compare the outcomes between the groups. Generalized logistic models will be used to adjust for covariates, gender and study site for these outcomes.

Dependent Variables	Variable Type	Analysis method
Insertion time	Continuous	Student t test
No insertion pain (yes, no); proximal colon adenoma detection (yes, no)	Binary	Chi square

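### The primary hypothesis claims lower pain in both men and women, but the SAP names one two-group test and no by-gender success rule

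*SAP*

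**What the plan says.** **The claim.** Protocol section (1)(b), Hypotheses, states: "Real-time maximum insertion pain (RTMIP) is significantly lower in both male and female Veterans examined by WECAC compared with WE". The Introduction of the abbreviated protocol agrees: "The goals are to determine if WECAC significantly reduces real-time maximum insertion pain (RTMIP) in both genders". The same Introduction also gives a gender-neutral aim, to "determine which method (with or without cap) is more effective in diminishing pain during the insertion of the colonoscope".

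**The sizing.** The SAP sizes each gender separately at a two-sided level of 0.0492. For men the per-group number "with 90% power is 72 or 144 total using a twosided two sample t-test"; for women it "with 90% power is 43 or 86 total using a two-sided two sample t-test". No combined sample size for RTMIP is given.

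**The test.** Under Primary hypothesis, the SAP restates the hypothesis for patients in general, without gender, and then says: "The analysis will compare 2 groups (WECAC vs. WE) with a two sample t-test". A Mann-Whitney test replaces the t-test if scores are clearly non-normal. Gender appears only in the secondary regression models.

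**Combined data.** At the end of the sample size text, pooling the genders is presented as a source of pilot information: "When the male and female data are combined, the sample size may reveal differences between WE and WECAC that are worth pursuing".

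**The interim.** Under Hypotheses Testing and Interim analysis, the same test is run at 0.0054 once half the subjects are evaluated, with no gender split. The first paragraph has the study stop on a significant result. The second sends the result to the DSMB for it to consider stopping.

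**The concern.** The claim, the sizing and the test do not describe the same analysis. The claim is a conjunction (men and women), the sizing is per gender, and the test as worded is a single comparison of two arms.

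A pooled comparison answers whether WECAC lowers pain on average over the enrolled mix. It does not inflate false positives for that question. It does not test whether each gender benefits, because a large enough effect in one gender can carry the result. A significant pooled test could then be reported as confirming the protocol's hypothesis when one gender gains nothing.

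If separate tests were intended, two things are still missing: whether both or either must be significant, and the power of the resulting rule. The same gap affects the interim, where a pooled crossing could end recruitment before either gender has its planned sample. Left open, the choice could be made after the results are seen.

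**Working it through.** **Inputs (SAP sample size paragraphs).** Men: WE 2.7 (SD 2.2), WECAC 1.5 (2.1), difference 1.2. Women: WE 6.2 (3.5), WECAC 3.5 (3.7), difference 2.7. Per arm: 72 men, 43 women. Two-sided levels: 0.0492 final, 0.0054 interim. Ranges below cover the planning SDs (2.2 and 3.7) and the arm-specific pilot SDs.

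**1. The plan's own figures.** At 90% power the t-test needs 71-72 men per group (0.55 SD, or 1.2/2.2) and 41-45 women (2.7/3.7, or 0.70 SD). The printed 72 and 43 are within 2 of these. Also 144/0.9 = 160 and 86/0.9 = 95.6, rounded up to 96.

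**2. Pooled test, one gender benefiting (planning SDs, normal approximation).**
- Within-gender variance: (72 × 2.2² + 43 × 3.7²)/115 = 8.149. The gender gap adds (72 × 43/115²) × gap² = 0.2341 × gap² in each arm.
- Women only: difference 43 × 2.7/115 = 1.010. Gaps are 3.5 (WE) and 0.8 (WECAC), so the arm variances are 11.02 and 8.30, SD 3.108, SE 3.108 × √(2/115) = 0.410. Ratio 2.46 against 1.967: power about 0.69.
- Men only: difference 72 × 1.2/115 = 0.751. Gaps are 3.5 and 4.7, variances 11.02 and 13.32, SD 3.488, SE 0.460. Ratio 1.63: power about 0.37.

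Simulation holds the gender counts fixed, as stratified randomization roughly does (40,000 normal-score trials per scenario; Mann-Whitney 10,000, normal and bounded 0-10 scores):

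| Share of trials favouring WECAC | Only men benefit | Only women benefit |
|---|---|---|
| Pooled t-test, pilot inputs | 34-35% | 70-73% |
| Pooled t-test, women's WE mean 1-2 points above men's, 44% reduction kept | 43-50% | 34-52% |
| Pooled Mann-Whitney | 49-76% | 52-70% |
| Both gender tests required | 2.5% or less | 2.5% or less |

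Counting both looks leaves the first row unchanged. The last row follows directly: the gender with no effect passes in WECAC's favour with probability 0.0492/2 = 0.0246, which caps the joint chance.

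**3. Joint power if both are required.** The genders are independent samples, so the powers multiply: 0.905 × 0.893 = 0.808 (0.55 and 0.70 SD), or 0.900 × 0.916 = 0.825 (1.2/2.2 and 2.7/3.7). Simulation gives 0.83-0.85, so the range is 0.81-0.85 (Mann-Whitney 0.79-0.92). With women's WE mean only 1-2 points above men's, it falls to 0.46-0.67.

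**4. If either gender could carry the claim.** Familywise error would be 1 − (1 − 0.0492)² = 0.096.

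**5. Interim at 0.0054, pooled t-test.** The gender mix is not stated, so it is assumed:

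| Men/women per arm | Pilot effects | Women only | Men only |
|---|---|---|---|
| 36/21 (160:96 target ratio) | 56-59% | 11-12% | 2-3% |
| 28/29 to 38/19 (1-2 men per woman, protocol subject availability table) | 54-64% | 9-27% | 1-3% |
| 50/7 (slow enrolment of women) | 50-53% | 1% | 18-20% |

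Mann-Whitney at 36/21 gives 50-80%, 7-12% and 4-12%. Under the pilot effects at 36/21, in 31-32% of t-test crossings the genders are not both significant even at 0.0492. Both truly benefit in that scenario, so this reflects low power by gender at half the sample. With both genders required at 0.0054, crossing falls to about 9-10%.

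**The case against.** The strongest reply is that separate tests were meant. The hypothesis names both genders, the protocol's primary outcome heading refers to men and women, each gender is sized for the very test and level that the analysis section names, and combined data are called pilot material. On that reading the pooled rates do not apply. This is a fair reading, but the analysis section does not state it, its hypothesis drops gender, and the gender-neutral aim in the Introduction points the other way. Even if it is right, the both-or-either rule and the joint power remain unstated, and the two rules differ greatly: about 2.5% or less false claims of benefit in both genders under one, 9.6% familywise error under the other.

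Second, a gender-by-group interaction is planned, since gender is in protocol Table 9 and the SAP tests covariate-by-group terms. With the pilot inputs it is significant in 95-96% of the women-only trials where the pooled test succeeds, so that case would rarely go unnoticed. It flags only 17-18% of the pooled-significant men-only trials, however, and is also significant in about half of trials when both genders benefit as in the pilot. No decision depends on it.

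Third, no text says that a pooled result would be reported as benefit in both genders. True, but that is the protocol's stated primary hypothesis, and this is the only test assigned to it.

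Fourth, the figures rest on nine women and on normal scores. That stands as a limit on the sizes, not on the gap in the plan.

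**Conclusion.** The concern holds. The named test, on its plain reading, does not match the primary hypothesis, and no by-gender decision rule or joint power is given in the SAP text available; one part of the SAP ahead of the general analytic plan could not be checked.

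The mismatch is material. At the final look the pooled test succeeds in at least 34% of trials when only one gender benefits, in every case examined, against about 2.5% or less if both are required. The exact rates are illustrative. Five WE women fix the gender gap (95% CI for their mean 1.9 to 10.5), and normal scores put 24-25% of WECAC men below zero on a 0-10 scale. The interim rates also depend on an assumed gender mix, and a crossing ends the trial only if the Hypotheses Testing wording prevails over the Interim analysis wording.

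**What to change.** **Needed.**
1. Reconcile the protocol hypothesis and goals, the two sample size paragraphs and the SAP primary analysis. Either:
   - keep the claim about both genders, and make the primary analysis two gender-specific tests, both required at 0.0492. No alpha split is needed. State that 90% is the power per gender and that joint power is about 81-85%; or
   - keep the pooled test, and limit its conclusion to the overall effect, not benefit in both genders.
2. State that the interim criterion follows the same rule, and reconcile the two SAP paragraphs on automatic stopping versus DSMB consideration.

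**Optional.** Estimate any overall effect with gender in the model, or use a gender-stratified rank test. Under the pilot gender gap the unstratified standard error is about 11% too large (0.418 against 0.376 with planning SDs).

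**Cost.** Only wording, if the sponsor accepts the lower joint power, which could be much lower if the female pilot effect is overstated. Under the both-required rule an interim crossing becomes rare (about 9-10% at 36/21), so the trial would usually run to full size. Restoring 90% jointly needs about 94.9% power per gender (√0.90): 87 + 54 or 89 + 50 per arm, so 282 or 278 evaluable and, after dividing by 0.9 and rounding up within gender, 314 or 310 recruited instead of 256. That increase is not proposed. The pooled option costs no power but gives up the claim about both genders.

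### The secondary mixed model for RTMIP tests gender by arm but allows no residual variance by sex; if the sizing SDs hold, a single variance puts that 5% test at about 8%

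*SAP*

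**What the plan says.** In the SAP, under Hypotheses Testing, Primary hypothesis, the primary comparison of RTMIP is a two-sample t-test, or a Mann-Whitney test if the data are clearly non-normal. A further analysis follows: "Secondary analysis of the primary outcome will utilize mixed effects regression models". Each covariate from Protocol Tables 9 and 10 is first examined in a model with arm, gender and the covariate-by-arm interaction. Covariates significant as a main effect or an interaction then enter a multiple regression. Gender is listed in Table 9, so gender by arm is one of these interactions.

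On variance structure the section adds only "We will include two levels of random effects in this model", namely site and provider within site. It does not mention the residual variance, variance by sex or robust standard errors.

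The SDs come from the SAP's two sample-size sections. RTMIP in the male pilot "was 2.7 (2.2) with WE (n=87) and 1.5 (2.1) with WECAC (n=38"). For women, "the PI identified 9 scheduled unsedated female Veterans (5 WE, 4 WECAC"), and "RTMIP were WE, 6.2 (3.5) and WECAC, 3.5 (3.7").

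The Statistical Analysis section says that assumptions will be checked. The remedies it names are a data transformation or a non-parametric test.

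**The concern.** A linear mixed model in its usual form, including Stata's default, has one residual variance for all patients. The plan's own figures put the residual spread in women well above that in men. Random effects for site and provider do not absorb this, because they describe differences between sites and providers, not a different scatter in men and women. Women are also the smaller group. A pooled variance borrows the men's precision for the women, so the standard error of the gender-by-arm term comes out too small.

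The protocol's primary hypothesis is a reduction in both sexes, and this model is the only named RTMIP analysis with a gender-by-arm term. The test also acts as a gate: a significant interaction brings the covariate into the final multiple regression. A test thought to run at 5% would admit it more often than intended.

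The remedies for failed assumptions do not repair this. A Mann-Whitney test does not give the regression interaction. A transformation changes the scale on which the interaction is judged. That matters here, because the plan expects the same 44% reduction in both sexes but different reductions in points (1.2 and 2.7).

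**Working it through.** **Inputs.** Male SDs are 2.2 (WE) and 2.1 (WECAC); female SDs are 3.5 and 3.7. Evaluable numbers per arm are 72 men and 43 women. All are from the SAP's sample-size sections. No site or provider variance is given, so those effects are left out. Arms are taken as balanced within sex.

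**The plan's own figures.** The relevant sentence begins "The sample size/group needed to detect a difference at a level of significance of 0.0492". For men, "2.7-1.5=1.2 is 1.2/2.2=0.55 standard deviation (SD) units"; a two-sided t-test at 90% power then needs 71.9, so 72 per arm, and 144/0.9 = 160. For women, "The reduction (44%) was 2.7/3.7 or 0.7 SD unit". The t-test needs 45 per arm at 0.70 SD or 41 at 2.7/3.7 SD; the normal approximation at alpha 0.05 and 0.70 SD gives 43, the plan's figure. 86/0.9 rounds up to 96. So the numbers used below are the plan's numbers, to within 2 per arm.

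**Variance ratio.** (3.5² + 3.7²)/(2.2² + 2.1²) = 25.94/9.25 = 2.80.

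**Single residual variance.** s² = (71 × 9.25 + 42 × 25.94)/226 = 7.73, so the residual SD is 2.78.

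**Standard errors of the arm difference, in points.**

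| | Separate variances | One variance |
|---|---|---|
| Men | √(9.25/72) = 0.358 | √(2 × 7.73/72) = 0.463 |
| Women | √(25.94/43) = 0.777 | √(2 × 7.73/43) = 0.599 |
| Gender by arm | √(0.358² + 0.777²) = 0.855 | √(0.463² + 0.599²) = 0.758 |

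**Level of the gender-by-arm test.** The standard-error ratio is 0.758/0.855 = 0.886. With critical value 1.97, the true level is 2 × P(Z > 1.97 × 0.886) = 8.1%. In 40,000 simulated trials it was 8.2% with normal data and 8.5% with scores bounded at 0 to 10. With separate variances the simulated level was 4.9%. At the recruited numbers (80 and 48 per arm) the calculation again gives 8.1%.

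**Sex-specific intervals, if anyone reads them from the model.** Nominal 95% intervals cover 87.2% in women (half-width 1.18 instead of 1.53) and 98.9% in men.

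**Average arm effect.** In an additive model, with weights 72/115 and 43/115, the standard error is 0.367 either way.

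**How firm are the SDs?** The pooled female SD is 3.59 on 7 degrees of freedom, with 95% limits 2.37 to 7.30. The female-to-male SD ratio is 1.65 (1.07 to 3.39; two-sided p = 0.023). These limits and the p-value assume normality.

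| Assumption | Gender-by-arm level | Female coverage |
|---|---|---|
| Sizing SDs | 8.1% | 87.2% |
| Female SD 3.0 | 6.9% | 89.9% |
| Female SD 2.5 | 5.8% | 92.9% |
| Female SD 2.4 | 5.5% | 93.5% |
| Male WE SD 3.0 (Protocol Table 5, row D) | 6.9% | 90.0% |

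**The case against.** The case on the other side has several sound parts.

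- **The single variance is not stated.** A reader might infer that the SAP prescribes one residual variance. It does not; it is silent, and one variance is only the usual default. The point is therefore conditional on that default.
- **Sex-specific intervals are not promised.** A reader might infer that the plan's error bars for men and women are wrong. The SAP uses this model to examine covariates and does not commit to sex-specific effects from it. Men and women were each sized for a two-sample t-test, and within-sex t-tests would use each sex's own variance. The coverage figures describe a possible use of the model, not a planned output.
- **The female SDs are weak evidence.** They rest on 5 and 4 patients, are raw rather than residual SDs, and one earlier male WE cohort had SD 3.0. The excess over 5% could be negligible. Against that, recalled pain shows the same pattern (SD 2 in men, 3 in women). The male means (2.7 and 1.5) also lie closer to the floor of the scale than the female means (6.2 and 3.5), so unequal spread is plausible.
- **Assumptions will be checked.** This stands, but neither named remedy corrects this test on the points scale.
- **The 8% is a level under the null.** It applies when the reduction in points is equal in the two sexes. The plan's own figures imply a difference of 2.7 − 1.2 = 1.5 points.

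What survives is narrower than a fault in the trial's main result, but it concerns a planned test that feeds model selection.

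**Conclusion.** The point holds as a free improvement to a secondary analysis. With one residual variance and the sizing SDs, the nominal 5% gender-by-arm test has a true level of about 8%. That falls to about 5.5% to 7% for female SDs of 2.4 to 3.0, and to about 7% with a male WE SD of 3.0. This rests on the conventional default, arms balanced within sex, and no allowance for site, provider or covariate effects.

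A reader might infer that the primary result is at risk. It is not: the primary test is a t-test or Mann-Whitney test outside this model, and the average arm effect keeps the same standard error. Nor do 9 women establish that the variances differ this much. They only make it imprudent to assume that the variances are equal.

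**What to change.** In the SAP's Primary hypothesis section, state that the RTMIP mixed model will have separate residual variances for men and women (in Stata, `residuals(independent, by(gender))`). State also that the gender-by-arm test, and any sex-specific estimates that are reported, will come from that model.

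Robust standard errors clustered by site should not be the substitute. The protocol lists three sites. In 4,000 simulated trials of a linear model with female SD 3.6, male SD 2.15, three near-equal sites and critical value 1.96, the nominal 5% gender-by-arm test rejected about 19% of the time with a small-sample factor and about 25% without. That is worse than the problem being fixed.

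The cost is one extra variance parameter and one sentence, with no extra patients or data. If the spreads prove equal, almost nothing is lost.
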